9.7.1.6.3 EXPLORATORY EFFICACY ANALYSES

Time to change of concomitant AD treatment will be analyzed similarly to that for time to conversion to dementia based on clinical diagnosis. Time to change of concomitant AD treatment is defined as time from randomization to the first dose increase and/or initiation of treatment with AChEI or memantine after randomization. For subjects without any change of concomitant AD treatment by the end of study, the time to change of concomitant AD treatment will be censored at the date of last assessment of concomitant medication.

The proportion of subjects with any change of concomitant AD treatment at 24 months will be analyzed similarly to that for proportion of subjects with dementia diagnosis at 24 months.

The rate of change over time (mean slope) based on change from baseline in the NPI-10 item will be analyzed in a manner similar to that used for the rate of change over time (mean slope) based on change from baseline in the CDR-SB.

The analysis of the following exploratory efficacy endpoints will be performed to compare elenbecestat versus placebo using the appropriate prespecified statistical methods including MMRM model, analysis of covariance model (ANCOVA), etc. For each exploratory efficacy endpoint, the treatment effect for elenbecestat 50 mg per day versus placebo will be tested at a significance level of 2-sided $\alpha = 0.05$.

- Change from baseline in NPI-10 item at 24 months
- Change from baseline in EQ-5D (subject self-reported, study partner self-reported, and subject measured by proxy) and QOL-AD (subject and study partner) at 24 months
- Change from baseline in Zarit's Burden Interview at 24 months

Additional analyses may be performed as needed.

9.7.1.7 Pharmacokinetic, Pharmacodynamic, Pharmacogenomic, and Other Biomarker Analyses

9.7.1.7.1 PHARMACOKINETIC ANALYSES

Safety Analysis sets will be used for individual elenbecestat plasma and CSF concentration listings. The PK Analysis Set will be used for the summaries of elenbecestat plasma and CSF concentrations.

A population PK approach will be used to characterize the PK of elenbecestat. The effect of covariates (ie, demographics) on elenbecestat PK will be evaluated. The PK model will be parameterized for clearance (CL) and volumes of distribution. Derived exposure parameters such as AUC will be calculated from the model using the individual posterior estimate of CL and dosing history.

9.7.1.7.2 PHARMACOKINETIC-PHARMACODYNAMIC

The PK/PD relationship between CSF biomarker levels and plasma PK parameters or CSF concentrations of elenbecestat will be explored graphically and any emergent relationship

will be explored through population PK/PD modeling. These PK parameters include maximum observed concentration (C_{max}), and $AUC_{(0-24)}$ derived from the population PK model. The PK/PD relationship between plasma PK parameters and CSF concentrations of elenbecestat with other biomarkers may also be explored using similar methods.

Additionally, the relationship between various PK parameters (eg, C_{max}) or CSF concentrations of elenbecestat and CDR-SB at 24 months, and the relationship between various PK exposure parameters or CSF concentrations of elenbecestat and the change from Baseline for 24 months in ADAS-cog14, and the MMSE, will be explored graphically. Any emergent relationships will be explored through population PK/PD modeling. The relationship between exposure to elenbecestat and most frequent AEs will also be explored.

9.7.1.7.3 PHARMACODYNAMIC, PHARMACOGENOMIC, AND OTHER BIOMARKER ANALYSES

The analysis of the biomarker endpoints defined as below will be performed to compare elenbecestat versus placebo using the appropriate prespecified statistical methods including MMRM model, ANCOVA, or non-parametric methods if the data is not normally distributed, etc. These analyses will be conducted without adjustment for multiplicity or sequential testing. For each endpoint, the treatment effect for elenbecestat 50 mg per day versus placebo will be tested at a significance level of 2-sided alpha = 0.05. (revised per Amendment 04)

- Change from baseline in tau PET signal at 24 months (revised per Amendment 04)
- Change from baseline in CSF biomarkers t-tau and p-tau at 24 months
- Change from baseline in CSF amyloid biomarkers $A\beta(1-42)$, and $A\beta(1-x)$ at 24 months (revised per Amendment 03)
- Change from baseline in total hippocampal volume at 12 and 24 months using vMRI
- Change from baseline in fMRI parameters as appropriate (revised per Amendment 05)
- Change from baseline in plasma amyloid biomarker (eg, $A\beta(1-x)$) at all assessments (revised per Amendment 05)
- Change from baseline in potential plasma and CSF biomarkers of AD (eg, NFL, VILIP1, YKL-40, and Ng) (revised per Amendment 05)

The relationship between exposure (in CSF, plasma) of elenbecestat with potential biomarkers of Alzheimer's disease as deemed appropriate will be evaluated using appropriate statistical model with the continuous changes in biomarker at 24 months as response variables and exposure variables (in CSF, plasma) of elenbecestat as independent variables.

9.7.1.8 Safety Analyses

Evaluations of safety will be performed on the Safety Analysis Set. The incidence of AEs, out-of-normal-range laboratory safety test variables, abnormal ECG findings, and out-of-range vital signs, suicidality, events of possible signals of drug abuse potential, results of the sleep questionnaire, along with change from baseline in laboratory safety test variables, ECGs, and vital sign measurements will be summarized by treatment group. (revised per Amendment 05)

9.7.1.8.1 EXTENT OF EXPOSURE

The Duration of exposure to study drug will be summarized as cumulative extent of exposure in categories with 3-month increment. The cumulative number and percent of subjects in each applicable exposure category will be presented by treatment group. Duration of exposure will be summarized using descriptive statistics as well as by 3-month duration categories using counts. The number and percent of subjects within each duration category will be presented by treatment group. Overall exposure (number of subject-months) is defined as summation over all subjects' exposure durations and will be summarized by treatment group.

9.7.1.8.2 ADVERSE EVENTS

The AE verbatim descriptions (investigator terms from the eCRF) will be classified into standardized medical terminology using the Medical Dictionary for Regulatory Activities (MedDRA). AEs will be coded to the MedDRA (Version 19.0 or higher) lower level term closest to the verbatim term. The linked MedDRA PT and primary system organ class (SOC) are also captured in the database.

A TEAE is defined as:

- An AE that emerges on or after start of study treatment, having been absent at pretreatment (Baseline) or
- Reemerges on or after start of study treatment, having been present at pretreatment (Baseline) but stopped before treatment, or
- Worsens in severity on or after start of study treatment relative to the pretreatment state, when the AE is continuous. (revised per Amendment 03)

Only those AEs that are treatment-emergent will be included in summary tables. All AEs, treatment-emergent or otherwise, will be presented in subject data listings.

The TEAEs will be summarized by treatment group on the Safety Analysis Set. The incidence of TEAEs will be reported as the number (percentage) of subjects with TEAEs by SOC and PT. A subject will be counted only once within an SOC and PT, even if the subject experienced more than 1 TEAE within a specific SOC and PT. The number (percentage) of subjects with TEAEs will also be summarized by maximum severity (mild, moderate, or severe). The number (percentage) of subjects with TEAEs will also be summarized by relationship to study drug (Yes [related] and No [not related]).

The number (percentage) of subjects with treatment-related TEAEs will be summarized by SOC and PT. Treatment-related TEAEs include those events considered by the investigator to be related to study drug. The number (percentage) of subjects with treatment-related TEAEs will also be summarized by maximum severity (mild, moderate, or severe).

AEs will be summarized by the following subgroups: region, prior treatment with AChEIs or memantine (no or yes), and clinical subpopulation (MCI due to AD or the early stages of AD).

The number (percentage) of subjects with TEAEs leading to death will be summarized by MedDRA SOC and PT for each treatment group. A subject data listing of all AEs leading to death will be provided. The number (percentage) of subjects with treatment-emergent SAEs will be summarized by MedDRA SOC and PT for each treatment group. A subject data listing of all SAEs will be provided. The number (percentage) of subjects with TEAEs leading to discontinuation from study drug will be summarized by MedDRA SOC and PT for each treatment group. A subject data listing of all AEs leading to discontinuation from study drug will be provided.

9.7.1.8.3 LABORATORY VALUES

Laboratory results will be summarized using International System of Units, as appropriate. For all quantitative parameters listed in [Section 9.5.1.5.3](#), the actual value and the change from baseline to each postbaseline visit and to the end of treatment (defined as the last on-treatment value) will be summarized by visit and treatment group using descriptive statistics. Qualitative parameters listed in [Section 9.5.1.5.3](#) will be summarized using frequencies (number and percentage of subjects), and changes from baseline to each postbaseline visit and to end of treatment will be reported using shift tables. Percentages will be based on the number of subjects with both nonmissing baseline and relevant postbaseline results.

Laboratory test results will be assigned a low/normal/high (LNH) classification according to whether the value was below (L), within (N), or above (H) the laboratory parameter's reference range. Within-treatment comparisons for each laboratory parameter will be based on 3-by-3 tables (shift tables) that compare the baseline LNH classification to the LNH classification at each postbaseline visit and at the end of treatment. Similar shift tables will also compare the baseline LNH classification to the LNH classification for the highest and lowest value during the Treatment Period.

[Appendix 1](#) (Sponsor's Grading for Laboratory Values) presents the criteria that will be used to identify subjects with treatment-emergent markedly abnormal laboratory values (TEMAVs). Except for phosphate, a TEMAV is defined as a postbaseline value with an increase from baseline to a Grade of 2 or higher. For phosphate, a TEMAV was defined as a postbaseline value with an increase from baseline to a Grade of 3 or higher. When displaying the incidence of TEMAVs, each subject may be counted once in the laboratory parameter high and in the laboratory parameter low categories, as applicable.

9.7.1.8.4 VITAL SIGNS

Descriptive statistics for vital signs parameters (ie, systolic and diastolic BP, pulse, respiratory rate, temperature, weight), and changes from baseline will be presented by visit and treatment group.

9.7.1.8.5 OTHER SAFETY ANALYSES

Cognitive decline will be assessed as a safety assessment, in addition to efficacy assessments. Cognitive assessments will include the ADAS-cog14, MMSE, and CDR. (see [Section 9.7.1.6](#)).

vMRI will be used to evaluate disease modification as indicated by measurements of brain atrophy, including the change from Baseline in terms of the measured hippocampal volume based upon the centralized measurement of the structure on repeated MRIs. A large number of studies, including the AD Neuroimaging Initiative, have shown that quantitative measurements of hippocampal, whole brain, and total ventricular volume provide robust and reliable biomarkers of disease progression, and potential for assessment of PD efficacy.

MRI sequences will be collected for all subjects at 12 and 24 months per the Schedule of Assessments. vMRI data will be analyzed at the Screening Visit and at Visits 9 and 13 (12 and 24 months of treatment). QC and normalization procedures for measurements of the whole brain, total ventricular volume, and right and left hippocampal volumes will be based on a validated algorithm and conducted in the same central laboratory. Additional analysis of regions of interest and cortical thickness may also be performed.

9.7.2 Determination of Sample Size

The sample size for this study is estimated for comparison of elenbecestat versus placebo with respect to a pooled analysis of studies E2609-G000-301 and E2609-G000-302 for the change from baseline in CDR-SB at 24 months. Based on the available data from the placebo group in Study BAN2401-G000-201 (a recently completed study with a comparable subject population), the mean and the standard deviation of the change from baseline in CDR-SB at 24 months in the placebo group are assumed to be 1.46 and 2.05, respectively, instead of 1.75 and 2.05, which are originally assumed by the available data from ADNI (of amyloid positive, MMSE equal or greater than 24, late MCI [global CDR=0.5, CDR memory box \geq 0.5]). Therefore, assuming a 25% reduction in the mean change from baseline CDR-SB at 24 months for elenbecestat compared to placebo with common standard deviation of 2.05 and 30% dropout rate, a total sample size of 1900 subjects, 950 subjects in each treatment group, will be required to detect the treatment difference between elenbecestat and placebo using a 2-sample t test with 90% power at a significance level of 2 sided alpha =0.05.

The pooled data from 2 studies (E2609-G000-301 and E2609-G000-302) will comprise the total sample size of approximately 1900 subjects. At least 850 subjects will be randomized in each study. (revised per Amendment 05)

9.7.3 Interim Analysis

This is a fixed design. There is no interim analysis of efficacy and no alpha spending before final analysis. However, a futility analysis is planned when approximately 30% subjects in the combined two studies (E2609-G000-301 and E2609-G000-302) have had an opportunity to complete the 24-month visit of the Core Study by the interim cutoff date. The sponsor

may stop the trial for futility with nonbinding futility boundary calculated using conservative O'Brien-Fleming boundary of Lan-DeMets alpha spending function with 30% information based on completers. If the actual percent information of the futility analysis is different from 30%, the futility boundary will be recalculated using the actual percent information at time of futility analysis. A blinded sample size re-estimation through estimated standard deviation based on blinded data before the completion of enrollment, will be performed if there is an indication that sample size assumptions need to be changed. This blinded sample size re-estimation could be performed based on signals from external studies or based on review of blinded data from this study before completion of enrollment. The standard deviation of the primary endpoint was originally estimated based on data from the ADNI study. It is possible that the standard deviation for the same endpoint in clinical trials may be larger than that from this observational study. (revised per Amendment 05)

An independent DSMB will convene at regular intervals to monitor the overall safety of the study and to make recommendations to the sponsor related to study safety as appropriate. The DSMB will be asked to review the cumulative safety data, which includes measures of cognitive safety at the group level, up to the date identified to make a determination if the trial is safe to proceed unchanged or to provide recommendations to the Sponsor as to how to proceed. The study will proceed, including randomization of additional subjects, during DSMB safety reviews. DSMB reviews will then continue to occur at regular intervals. Details will be provided in the DSMB Charter. (revised per Amendment 05)

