9.7.1 Statistical and Analytical Plans

All statistical analyses will be performed by the Sponsor or designee after the study is completed and the database is locked and released for unblinding. All statistical analyses will be performed based on the pooled data from 2 studies (E2609-G000-301 and E2609-G000-302). The analyses will also be performed within each study to confirm the trend of the efficacy and biomarker endpoints unless specified. (revised per Amendment 05)

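### Section 9.7.3 derives the nonbinding futility boundary from an alpha-spending function, which gives an efficacy bound (|Z| = 3.93 at 30% information), and does not say which side means futility

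*Protocol*

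**What the plan says.** Section 9.7.3 calls the design fixed and states: "There is no interim analysis of efficacy and no alpha spending before final analysis". It then plans a futility look when about 30% of subjects in studies 301 and 302 combined have had the chance to reach the 24-month visit. The sponsor may stop on a nonbinding boundary, described as conservative and taken from the O'Brien-Fleming "boundary of Lan-DeMets alpha spending function with 30% information based on completers". If the actual information differs from 30%, the boundary is recomputed. The synopsis repeats this under Interim Analyses. Neither place gives a beta-spending function, a conditional- or predictive-power threshold, a Z value, or the direction of the rule.

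The design inputs are in section 9.7.2. The placebo mean change and standard deviation of CDR-SB at 24 months "are assumed to be 1.46 and 2.05, respectively". The effect comes from "assuming a 25% reduction in the mean change from baseline CDR-SB at 24 months", with "common standard deviation of 2.05 and 30% dropout rate". The 1900 subjects are sized "using a 2-sample t test with 90% power at a significance level of 2 sided alpha =0.05".

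**The concern.** An alpha-spending function allocates type I error over looks, and its boundary is the point at which the null may be rejected early. A futility boundary is a different object. It comes from spending type II error, from conditional or predictive power, or from a stated effect threshold. The protocol does not leave this choice open: it names the function, its shape and the information fraction, and the type of function is wrong.

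This is the only prespecified rule in the protocol for stopping the two pooled studies on efficacy data. Two statisticians applying the sentence literally could reach opposite recommendations from the same interim data, because the side that means futility is not stated.

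**Working it through.** Positive Z favours elenbecestat throughout.

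**1. Reproduce the sample size.** Difference = 0.25 × 1.46 = 0.365. Per arm, n = 2 × (1.960 + 1.282)² × 2.05² / 0.365² = 663. Allowing for 30% dropout, 663 / 0.70 rounds up to 948, or 1896 in total against the stated 1900. The inputs are therefore the protocol's own. With 950 per arm, completers are 0.70 × 950 = 665 per arm.

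**2. Expected Z at the look.** Final standard error = 2.05 × √(2/665) = 0.1124, so the expected final Z is 0.365 / 0.1124 = 3.247. At information t = 0.30 it is 3.247 × √0.30 = 1.778. The interim standard error is 2.05 × √(2/199.5) = 0.205.

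**3. The function as named.** With 0.025 per side, alpha spent = 2 × [1 − Φ(2.241/√0.30)] = 0.0000427. The bound is |Z| = 3.93, an observed difference of 3.93 × 0.205 ≈ 0.81 points, more than twice the design effect.

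**4. The same shape as beta spending, total beta 0.10.** Beta spent = 2 × [1 − Φ(1.645/√0.30)] = 0.0027. The corresponding normal quantile is 2.785, so the bound is 1.778 − 2.785 = −1.01, about 0.21 points in favour of placebo.

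**5. Probability of a stop signal at 30% information.**

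| Rule | No effect | Design effect (0.365) |
|---|---|---|
| Stop if Z ≤ −3.93 | 0.004% | about 6 × 10⁻⁹ |
| Stop unless Z reaches 3.93 | 99.996% | Φ(3.929 − 1.778) = 98.4% |
| Beta spending, stop if Z ≤ −1.01 | about 16% | 0.27% |

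The first rule stops only 1.6% of the time even if the drug is harmful by the full 0.365 points.

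**6. Power if the signal is always obeyed (simulated, 2 million runs).** No look: 90.1%. Lower bound −3.93: 90.1%. Hurdle at 3.93: 1.6%. Beta-spending bound: 90.0%.

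**7. Sensitivity.** At 25% and 35% information the alpha-based lower bound stops an ineffective drug with probability 0.0007% and 0.015%. The alpha-based hurdle signals a stop for an effective drug with probability 99.7% and 95.5%. Placing 0.05 in one tail gives |Z| = 3.39 at 30% information, with 0.035% and 94.7% respectively.

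**The case against.** The strongest reply is that the sentence contains one wrong word. The boundary is called nonbinding, conservative and for futility, and the section says no alpha is spent. Together these point to an O'Brien-Fleming-shaped function meant for the futility side, which step 4 shows to be workable. This stands as a reading of intent. It also disposes of any supposed clash with "There is no interim analysis of efficacy and no alpha spending before final analysis": a nonbinding futility look spends no alpha, so that statement is right for the design and is evidence of a naming slip. It does not rescue the rule as printed, which yields 3.93 and no direction.

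It is also fair that the hurdle reading is not stated anywhere and sits badly with the word conservative. A reader might infer that the rule would end development of an effective drug almost surely. The text does not support that, because the sponsor may stop and need not.

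A reader might infer three governance faults as well. The documents do not support them:

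- **A sponsor-run unblinded look.** Section 9.7.3 gives the sponsor the decision and does not say who runs or sees the comparison. Section 9.4.6 keeps sponsor staff blinded through the Randomization and Follow-up Phases.
- **A DSMB confined to safety.** The sentence beginning "The DSMB will be asked to review the cumulative safety data" goes on to include group-level cognitive safety measures, and section 9.7.1.8.5 counts ADAS-cog14, MMSE and CDR among the cognitive assessments.
- **A conflict with database lock.** "All statistical analyses will be performed by the Sponsor or designee after the study is completed and the database is locked and released for unblinding" is a general statement, and section 9.7.3 openly introduces the futility look as a specific exception.

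**Conclusion.** The point holds as a wrongly specified decision rule. Taken literally, the named function has no useful operating characteristics for futility: about 0.004% chance of stopping under no effect on one reading, and about a 98% chance of signalling a stop under the design effect on the other. This does not depend on the look falling at exactly 30%.

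The consequences have limits. The boundary is nonbinding, so the second reading would signal a stop without forcing one. The first reading wastes the look but leaves the final test and its power intact. Type I error is not inflated on any reading.

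The figures rest on the section 9.7.2 assumptions, 665 completers per arm, a normal approximation for the interim statistic, and 0.025 per side. The SAP and DSMB charter were not available. If either holds a sensible bound, it would differ from the protocol, and the protocol sentence would still need correcting.

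**What to change.** In section 9.7.3 and in the synopsis, replace the alpha-spending function with a nonbinding O'Brien-Fleming-type Lan-DeMets beta-spending function with total beta 0.10, keeping the existing provision to recalculate at the actual information. State the direction: stop may be considered if Z falls at or below the bound. Give the 30% case as reference: Z about −1.01, with stop probabilities of about 16% under no effect and 0.27% under the design effect.

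The cost is a short wording change in two places. It needs no extra patients and no alpha, and power if the rule is always obeyed is 90.0% against 90.1% with no look.
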